10.10 Treatment-related Adverse Events

Any AE with a relationship to study treatment of "Related" or missing will be considered a treatmentrelated AE as determined by the Investigator.

- 10.11 Imputation of AE and Concomitant Medication Start and Stop Dates
 - Start Date:
 - If only 'day' is missing, and the month and year are not the same as the month of first dose, then the day will be imputed with 1 (first day of the month). Otherwise, if the month and year are the same as the dose date, the day will be imputed with the day of the first dose of treatment.
 - If 'day' and 'month' are missing, and 'year' is not missing, then the missing month and day will be imputed with the month and day of the first dose date (assuming same 'year').
 - If 'day' and 'month' are missing and 'year' is not missing and is not the same year as first dose date, then the day and month will be imputed with the 1st of January.
 - Stop Date:
 - If only 'day' is missing, the day will be imputed with the last day of the month.
 - If 'day' and 'month' are missing, and 'year' is not missing, then the day and month will be imputed by the 31st of December (or by the date of study discontinuation or completion if earlier than the 31st of December and year is the same as the year of discontinuation).
 - If the stop date is completely missing and the AE/medication is not ongoing, it will be set to the date of study discontinuation or completion.

The imputed dates will be used to assess whether AEs should be considered as treatment-emergent and if medications should be included in the safety summaries as prior or concomitant medications. The original partial dates will be included in data listings.

The duration of AEs will be derived as the AE end date [(including imputation date for incomplete AE end date) – AE onset date (imputed date for incomplete AE onset date) + 1].

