If participant discontinues from the study early (ET) or withdraws from taking CLTX-305 (encaleret) (EoT), perform related assessments, resume prior medication regimen, arrange FU labs within 1-2 days. Participants instructed to obtain outpatient laboratory testing (See Footnote 10) approximately 1-2 days after discharge from NIH CC. PI/Site

- staff should contact the participant within 3-5 days to review test results and provide guidance regarding clinical management as they transition to prior clinical care providers. Optionally, participants may stay in the NIH CC overnight to complete assessments.
-  Including CaSR mutational analysis (if not documented).
-  Safety Labs Chemistry (Na, K, Cl, bicarbonate, Glu, BUN, Cr, alb, total protein, Ca, Mg, PO4, iPTH, 25-OH Vitamin D, cholesterol, TG, AST, ALT, Tbili, Alk phos, LDH, amylase, lipase, uric acid), Hematology (RBC, Hgb, Hct, RBC indices, WBC, diff), Coagulation (PT/PTT/INR), urinalysis. HIV, viral hepatitis panel, and iron panel to be done at screening visit only unless repeat measures are clinically indicated.
-  Height measured at screening only.
- Vital signs include supine or sitting blood pressure (BP) by automated cuff, heart rate (HR), and respiratory rate, to be collected q8 hours during in-patient days. Orthostatic BP and HR will be assessed once at screening and once daily during Period 2.
- Discontinue calcitriol on Day -1 during the admission.
- Initial dose (Days 1 & 2) of CLTX-305 (encaleret) BID based on results from Period 1. If calcium has not increased into the normal range, then the CLTX-305 (encaleret) dose will be increased for Days 3-5. Participants will undergo frequent PK/PD sampling over 24h on Day 5.
-  24-hour urine at the screening visit 14 to 10 days prior to Day 1 dosing (Ca, Mg, PO4, Cr, Na, K, Citrate, pH)
- For cohorts 1 and 2: outpatient laboratory testing on days -14 to -10 before admission include: blood Cr, Ca, Alb, Mg, PO4, 25-OH Vitamin D, Hematology (RBC, Hgb, Hct, RBC indices, WBC)
- 11 Interval lab tests at outpatient laboratory will be done in those for whom the screening visit is >21 days prior to Period 2.
- After the last dose of CLTX-305 (encaleret), for participants continuing to Period 3, dispense supply of CLTX-305 (encaleret) before discharge.

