# 8.5.5 Adverse Event Reporting

Any untoward event that is reported from the time that the study participant signs the ICF until  $30 \pm 7$  days after the last dose of CLTX-305 (encaleret) must be collected. Thus, any untoward medical occurrences or unfavorable and unintended signs, symptoms, or diseases that occur in the pretreatment, treatment, or posttreatment period are to be considered AEs (and SAEs if appropriate), and consequently recorded and reported as such.

Participants are to be queried regarding any AEs or SAEs at the time of each vital sign assessment, as well as at each visit, according to the Schedule of Activities (Section 1.3). Participants will be asked to volunteer information with a nonleading question such as, "How do you feel?" Study center personnel will then record all pertinent information in the participant's CRF.

All AEs and SAEs reported by the participant (or participant's legal representative) or observed or otherwise identified by the investigator (or other study center personnel) at a defined study visit or during any communication with the participant (or participant's legal representative) occurring outside a defined study visit (from the time the participant signs the ICF to  $30 \pm 7$  days after the last dose of CLTX-305 (encaleret) must be documented.

All AEs must be recorded on the appropriate AE reporting page of the participant's CRF whether or not they are considered causally related to the CLTX-305 (encaleret).

For every AE, the investigator must:

- Provide an assessment of the severity, causal relationship to CLTX-305 (encaleret), and seriousness of the event (i.e., whether it is a SAE)
- Document all actions taken with regard to CLTX-305 (encaleret)
- Detail any other treatment measures taken for the AE

Document resolution of the AE (with or without sequelae); ongoing; or lost to follow-up.

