10.8 Treatment-emergent Adverse Event (TEAE)

For subjects in Cohort 1, AEs will be considered treatment-emergent to Period 1 if they have missing or partial start dates for which it cannot be determined whether the AE started before or after the Period 1 or Period 2 first dose of study medication.

For subjects in Cohort 2, AEs will be considered treatment-emergent to Period 2 if they have missing or partial start dates for which it cannot be determined whether the AE started before or after the Period 2 first dose of study medication.

As there will be no interruption of study drug treatment between Period 2, Period 3 and LTE, those 3 periods will be considered only one period and referred to Period 2 in the below definitions.

Period 1

Treatment-emergent AEs (TEAEs) are defined as any AE(s) or SAE(s), regardless of relationship to study drug, that have an onset or worsening in severity on or after the first dose of study drug until 30 days after Period 1 last dose of treatment date.

Period 2

TEAEs are defined as any AE(s) or SAE(s), regardless of relationship to study drug, that have an onset or worsening in severity on or after the Period 2 first dose of study drug until 30 days after the last dose of treatment in the study.

Each AE is mapped to a Period based on their start date, using the rules defined in Table 2. If the start date is partial, determination of the Period will based on the imputed start date (see Section 10.11 for details). If the date is entirely missing, the AE will be assigned to Period 1 for subjects in Cohort 1 and to Period 2 for subjects in Cohort 2.

Cohort	Analysis Period	Start of the Period	End of the Period
	1*	Data of ICE	If the subject continued in Period 2: last dose in Period 1 + 30 days.
	1.	Date of ICF	If the subject did not continue in Period 2: all AEs are assigned to Period 1.
1	2	Date of Outpatient	If the subject continued in Period 3: last dose in Period 2.
	2	Admission Visit	If the subject did not continue in Period 3: Date of completion/discontinuation of the study
	3	Last dose date in Period 2 + 1 day	If the subject continued in LTE: last dose in Period 3.
			If the subject did not continue in LTE: Date of completion/discontinuation of the study
	LTE	Last dose date in Period 3 + 1 day	Date of completion/discontinuation of the study
	2		If the subject continued in Period 3: last dose in Period 2.
2	2	Date of ICF	If the subject did not continue in Period 3: all AEs are assigned to Period 2.

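### SAP 10.11 can set a partial start date later than the recorded stop date, so a record that ended before dosing is classed as concomitant or treatment-emergent

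*SAP*

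**What the plan says.** SAP 10.11 gives one set of date rules for AEs and medications. If only the day of the start date is missing, "if the month and year are the same as the dose date, the day will be imputed with the day of the first dose"; in any other month the first of the month is used. If only the year is known and it is the first-dose year, "then the missing month and day will be imputed with the month and day of the first dose date"; in any other year 1 January is used. No start-date rule refers to the stop date.

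Stop dates are imputed separately and late: "If only 'day' is missing, the day will be imputed with the last day of the month". The section then states that "The imputed dates will be used to assess whether AEs should be considered as treatment-emergent", and gives the imputed dates the same role for prior and concomitant medications. AE duration is the end date minus "AE onset date (imputed date for incomplete AE onset date) + 1".

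The classification rules work on the start date:

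- SAP 10.8 counts as Period 1 TEAEs those "that have an onset or worsening in severity on or after the first dose of study drug until 30 days after Period 1 last dose". It sets no end-date condition.
- SAP 10.7 and Table 1 make a medication concomitant if it starts on or after first dose. The 10.7 text requires a start before treatment for a medication to be prior.
- SAP 10.8 also says that a partially dated AE counts as treatment-emergent when one cannot tell on which side of first dose it began.

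Protocol 8.5.5 collects "Any untoward event that is reported from the time that the study participant signs the ICF", and Protocol 8.1 puts AEs before dosing in a Baseline category.

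**The concern.** Setting an unknown onset to the first-dose date is a reasonable cautious convention when the timing is unknown. It is not reasonable when the record itself shows that the event or drug had ended before dosing, because the stop date then settles the question. Under 10.11 such a record gets a start after its stop and moves into the on-treatment tables.

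Records of this kind are foreseeable. AEs are collected from consent, and screening may take place up to 60 days before admission. Protocol 8.1 lets investigators adjust regimens during screening, and Protocol 6.5 has thiazides stopped before dosing. What is at stake is the accuracy of the TEAE and concomitant-medication tables in a study of about 16 treated participants, and whether the derived AE durations make sense.

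**Working it through.** No figure in the plan depends on this rule, so there is nothing to reproduce first. The check applies 10.11 literally to test records. The first-dose date of 15 June 2021 is an assumption, used only for illustration.

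**Formula.** Duration = stop − imputed start + 1. The record is on treatment if its imputed start is on or after first dose.

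| Recorded start | Recorded stop | Imputed start | Stop used | Duration in days (if an AE) | Class by start date |
|---|---|---|---|---|---|
| June 2021, day missing | 5 June 2021 | 15 June | 5 June | 5 − 15 + 1 = −9 | on treatment |
| 2021 only | 20 April 2021 | 15 June | 20 April | −56 + 1 = −55 | on treatment |
| 2021 only | April 2021, day missing | 15 June | 30 April | −46 + 1 = −45 | on treatment |
| May 2021, day missing | 20 May 2021 | 1 May | 20 May | 20 − 1 + 1 = 20 | before treatment |
| June 2021, day missing | June 2021, day missing | 15 June | 30 June | 30 − 15 + 1 = 16 | on treatment |
| 2020 only | 14 June 2021 | 1 January 2020 | 14 June | 531 | before treatment |

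The first three rows are wrong: the stop date shows that each record ended before dosing. The fourth and sixth are classified correctly. The fifth is truly ambiguous, and treating it as on treatment is the intended caution.

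**Every pre-dose stop day.** With the day missing in the first-dose month, start falls after stop for 4 of 4 pre-dose stop days if dosing is on the 5th, 14 of 14 on the 15th and 27 of 27 on the 28th. With a year-only start and a 15 June dose, it does so for 165 of 165. A stop on the day before dosing gives a duration of −1 + 1 = 0, and any earlier stop gives a negative one.

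**Effect on a table row.** One participant wrongly added to a row changes it by 1/16 = 6.3 points with about 16 treated, or 1/8 = 12.5 points in Period 1 with 8. This applies only if the participant has no other record in that row, because SAP 13.6.1 counts each subject once per SOC or PT.

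**What is not affected.** Table 2 starts the first analysis period at the ICF date in each cohort, so a pre-dose AE already maps there. Moving its start to Day 1 does not change the all-AE count. The cCa and urinary calcium analyses do not use these dates.

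**With the start capped by the stop date.** The first test record starts on 1 June, lasts 5 − 1 + 1 = 5 days and is not on treatment. As a medication, the second starts on 1 January and is prior. As an AE it needs a floor, because 1 January gives a 110-day duration and can precede consent. If the ICF is assumed to be signed on Day −60 (16 April), the AE starts that day and lasts 20 − 16 + 1 = 5 days. In the same enumeration, setting the start to the earliest date the recorded part allows whenever the stop is before dosing leaves no inverted dates.

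**The case against.** The strongest reply concerns AEs. The wording of 10.8 makes a partially dated AE treatment-emergent when its timing cannot be established, and a recorded pre-dose stop does establish it. Protocol 8.1 calls such an AE Baseline, and SAP 13.6.1 requires first occurrence or worsening after first dose. This stands in part: it would be too strong to say that no rule guards against the error for AEs. But 10.8 says when to include an AE, not when to exclude one, and does not mention stop dates, while 10.11 gives the decision to the imputed date. The two sections conflict. Medications have no counterpart to this wording.

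A reader might infer that calcitriol will routinely appear as on-treatment use, since the protocol's schedule says "Discontinue calcitriol on Day -1 during the admission". The documents do not support that. Calcitriol is standard long-term therapy, and a start in an earlier year goes to 1 January of that year and stays prior; only a partial start in the first-dose year is caught. Cohort 1 participants also resume calcitriol at Period 1 discharge. If that is recorded as a new start, Table 1 properly counts it as Period 1 concomitant.

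A reader might also take the share of a 60-day pre-dose window that falls in the first-dose month (about 25%) or year (about 92%) as an error rate. It is not one: it assumes uniform onset and ignores whether dates are partial and whether a pre-dose stop was recorded.

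It is also fair that the error over-counts rather than hides TEAEs, that data queries should keep partial dates few, that no AE duration summary is planned, and that listings show the original partial dates. These points limit the impact but do not make the rule right.

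**Conclusion.** The concern holds within limits. As written, 10.11 classes a medication with a recorded pre-dose stop as concomitant and removes it from the prior category for that period. It classes an AE with a recorded pre-dose stop as treatment-emergent with an impossible duration, against 10.8 and the protocol's Baseline category.

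A reader might infer that the primary safety endpoint as a whole is distorted. SAP 9.0 states that endpoint as subjects with AEs and SAEs, and those all-AE counts do not change; the TEAE tables do.

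The number of records affected is unknown. The shift of up to 6.3 points per record (12.5 in Period 1) assumes 16 and 8 treated participants and no other record for that participant in the row. The text of SAP 10.13 and 10.15 was not available for this check, so nothing is concluded from those sections. The point is worth correcting because a stated rule gives a wrong answer that the data already contradict.

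**What to change.** In SAP 10.11:

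- Use the first-dose date for a partial start only if the stop date is missing, ongoing, or on or after first dose.
- Otherwise use the earliest date consistent with the recorded part, never later than the stop date and, for AEs, not earlier than the ICF date. Without that floor, a 1 January start could fall before the first Table 2 period and map to no period.
- State that a record whose stop date is before the first dose of study drug is never treatment-emergent or concomitant.

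Align 10.8 by saying that a stop date before first dose settles the timing. Because 10.11 imputes a missing stop day to the month end, an imputed stop before first dose can be used in the same way.

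The cost is a few sentences in the SAP and a small change to the date-imputation program. No new data are needed, and truly ambiguous records keep their present cautious handling.

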10.12 Analysis Visit Window

For initial screening the target day is -60 to -2 days before baseline. The visit will be mapped to screening if study day is -61 to -1 days. For Periods 1 and 2 once subjects are admitted to the inpatient facility, analysis will be performed for the day/time as scheduled.

For Period 3 and LTE, since the actual visit for a subject may not exactly coincide with the scheduled visit date, the actual visit date will be mapped to the study analysis visit as follows.

Analysis Visit	Target Day	Study Day	Interval (days)
Week 1	13	13	7 - 16
Week 2	20	20	17 - 23
Week 3	27	27	24 - 30
Week 4	34	34	31 - 41
Week 6	48	48	42 - 55
Week 8 (NIH visit)	62	62	56 - 76
Week 12	90	90	77 - 104
Week 16 (NIH visit)	118	118	105 - 132
Week 20	146	146	133 - 160
Week 24 (NIH visit)	174	174	161 - 188
Follow-up* (2-3 days post last dose)	No analysis visit window applies		
Follow-up* (7 days post last dose)	No analysis visit window applies		dow applies
Follow-up* (30 days post last dose) No analysis visit window applies		dow applies	

Table 3: Period 3 Analysis Visit Windows

* Follow-up visits are only performed if the subject does not continue in the LTE.

For the LTE, subjects will continue CLTX-305 (encaleret) per the dosing regimen established in the maintenance phase of Period 3. Telephone contacts along with outpatient laboratory assessments will be performed every 6 months starting at Month 3 with NIH inpatient visits occurring every 6 months starting at Month 6. The actual visit date will be mapped to the study analysis visit as follows.

Table 4: LTE Analysis Visit Windows

Analysis Visit	Target Day	Study Day	Interval (days)
Month 3	264	264	189 - 309
Month 6	354	354	310 - 399
Month 9	444	444	400 - 489
Month 12	534	534	490 - 579
Month 15	624	624	580 - 669
Month 18	714	714	670 - 759
Month 21	804	804	760 - 849
Month 24	894	894	850 - 939
Follow-up (2-3 days post last dose)	No analysis visit window applies		
Follow-up (7 days post last dose)	No analysis visit window applies		
Follow-up (30 days post last dose)	Ν	lo analysis visit win	dow applies

For assessments where more than one actual visit falls within the same defined window and it is not an inpatient NIH visit (Weeks 8, 16 and 24, Months 6, 12, 18 and 24), the visit closest to the target day with non-missing data will be considered for analysis. If two actual visit dates are at the same distance from the target day, the latest visit with non-missing data will be considered for analysis. If the scheduled visit is an inpatient NIH visit, the NIH inpatient visit will be considered for analysis.

All summaries and analyses will utilize analysis days/visits, where appropriate. Data listings will present actual day/visit names as recorded in the clinical database.

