Abbreviations: Adverse Event = AE; Albumin = Alb; Alanine aminotransferase = ALT; Blood urea nitrogen = BUN; Aspartate aminotransferase = AST; Alkaline Phosphatase = Alk Phos; Electrocardiogram = ECG; BID = Twice daily; Blood Pressure = BP; Calcium = Ca; Calcium Sensing Receptor = CaSR; Chloride = Cl; Concomitant medication = Con. meds; Creatine Kinase = CK; Creatinine = Cr; C-telopeptide = CTX; Dual-energy X-ray Absorptiometry = DXA; Early Termination = (ET); End of Treatment = EoT; Follow-up = FU; Follicle-Stimulating Hormone = FSH; Glucose = Glu; Heart Rate = HR; Hematocrit = Hct; Hemoglobin = Hgb; Lactate Dehydrogenase = LDH; Intact

Parathyroid Hormone = iPTH; Magnesium = Mg; National Institute of Health Clinical Center = NIH CC; Parathyroid Hormone = PTH; Phosphate = PO4; Phosphorus = P; Potassium = K; Pharmacodynamic = PD; Pharmacokinetic = PK; Procollagen type 1 N-propeptide = P1NP; Prothrombin Time/ Prothrombin Time = PT/INR; Red Blood Cell Count = RBC; Thromboplastin Time = PTT; Serious Adverse Event = SAE; QD = Once daily; Total Bilirubin = Tbili; Triglycerides = TGL; White Blood Count = WBC; Women Of Child Bearing Potential = WOCBP

- If participant discontinues from the study early (ET) or withdraws from taking CLTX-305 (encaleret) (EoT), before completing LTE per protocol, participant will be asked to return to the NIH CC within 30 days following the last dose for the ET/EoT visit assessments and return the unused CLTX-305 (encaleret). Participant should resume oral calcium and active vitamin D under the supervision of the study team while the encaleret is being safely discontinued. Follow-up labs should beperformed per this Schedule of Assessments.
- Participants who withdraw from taking CLTX-305 (encaleret) (EoT) before transitioning to the CLTX-305-302/CALIBRATE LTE per protocol will obtain the following outpatient laboratory assessments after the last dose of CLTX-305 (encaleret) and after re-starting their prior regimen of oral calcium and active vitamin D: blood Cr, Ca, Alb, Mg, iPTH, PO4. Follow-up (FU) call should occur within 3-5 days to review the lab results and receive guidance on clinical management of their ADH1 as participants transition to prior standard of care.
-  Unscheduled visits: For laboratory evaluation following dose adjustment or assessment or follow-up of an AE, in which clinically indicated procedures will be performed

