- Document current CLTX-305 (encaleret) dose and calcium dosing regimen, any modifications, and reason for modifications
- Outpatient laboratory testing: Blood samples for clinical laboratory panels (Na, Cl, bicarbonate, K, BUN, Cr and including Alb, Ca, Mg, PO4, iPTH, CTX, and P1NP).
-  Height measured only at month 24/final visit or ET visit
- Vital signs include supine or sitting blood pressure (BP) by automated cuff, heart rate (HR), and respiratory rate.
- Safety and Drug Monitoring Labs collected at the NIH CC visits approximately 4 hours after the morning encaleret dose Chemistry (Na, K, Cl, bicarbonate, Glu, BUN, Cr, Alb, total protein, Ca, Mg, PO4, iPTH, 25-OH Vitamin D, CTX, P1NP, Cholesterol, TG, AST, ALT, Tbili, Alk phos, LDH, amylase, lipase, uric acid, CK), Hematology (RBC, Hgb, Hct, RBC indices, WBC, diff), Coagulation (PT/PTT/INR), Research labs (FGF23 and mid-molecule PTH). HIV, viral hepatitis panel should be repeated within 3 months prior to transition to CLTX-305-302/CALIBRATE.
- 9 Blood β-HCG pregnancy test can be performed at the NIH CC on the day of transition to CLTX-305-302/CALIBRATE Phase 3 LTE, and an aliquot will also be sent to the central lab for the CLTX-305-302/CALIBRATE Phase 3 LTE.
-  CLTX-305 (encaleret) administered and recorded during the NIH CC visit/in-house days.
- Outpatient 24-hr urine collection for Ca, Mg, PO4, Cr, Na, K, citrate, pH
- A final follow-up safety telephone call and outpatient labs will occur 30 ± 7 days after the last dose of CLTX-305 (encaleret).
- 13 If a participant is not able to enter the LTE immediately following Period 3, then participant will be reconsented to and may restart CLTX-305 (encaleret) at the previous therapeutic dose determined in Period 3. Safety and Drug Monitoring Laboratory tests should be done while participant is at the NIH CC.
- When participant transitions to CLTX-305-302/CALIBRATE Phase 3 LTE, participant will be asked to return to the NIH CC to return the unused CLTX-305 (encaleret), and complete any remaining eligibility assessments for the CLTX-305-302/CALIBRATE Phase 3 LTE study.
- 15 If the Month 24 visit aligns with the transition to the CLTX-305-302/CALIBRATE Phase 3 LTE, then the renal ultrasound and DXA scan will be performed once as part of the CLTX-305-302/CALIBRATE Phase 3 LTE.

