### Transition to CLTX-305-302/CALIBRATE Phase 3 Long Term Extension

Participants from CLTX-305-201 who meet the study screening eligibility criteria of the CLTX-305-302/CALIBRATE Phase 3 study will enroll directly into the CLTX-305-302/CALIBRATE Phase 3 LTE. If assessments for 25-OH Vitamin D, eGFR, 12-lead resting ECG, viral hepatits panel and HIV have been completed either at the NIH CC or via outpatient lab within the 3 months prior to transitioning into the CLTX-305-302/CALIBRATE LTE, they do not need to be repeated for eligibility purposes. Other assessments performed during the final CLTX-305-201 ET/EoT study visit will be acceptable for assessment of CLTX-305-302/CALIBRATE eligibility criteria. Blood  $\beta$ -HCG pregnancy test can be performed at the NIH CC on the day of transition to CLTX-305-

302/CALIBRATE Phase 3 LTE, and an aliquot will also be sent to the central lab for the CLTX-305-302/CALIBRATE Phase 3 LTE.

If a participant discontinued encaleret during the CLTX-305-201 LTE for family planning purposes, the participant may enroll directly into the CLTX-305-302/CALIBRATE Phase 3 LTE once family planning is complete if he/she meets the study eligibility criteria per the CLTX-305-302/CALIBRATE protocol and the CLTX-305-302/CALIBRATE Encaleret Resumption Criteria. Participants will resume encaleret as described in the CLTX-305-302/CALIBRATE protocol.

Assessments in the CLTX-305-302/CALIBRATE Phase 3 LTE will be conducted approximately every 3 months as described in CLTX-305-302/CALIBRATE protocol's Schedule of Assessments. Participants who transfer to the CLTX-305-302/CALIBRATE Phase 3 LTE will receive encaleret for an additional period of approximately 48 months or until participant has access to commercial encaleret, or the Sponsor decides to end the study, whichever occurs first.

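### The LTE early-termination visit may come up to 30 days after the last dose, yet SAP 10.12 does not exempt it from the Month 3–24 windows, so off-drug values could enter the durability summaries

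*SAP*

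**What the plan says.** **Timing of the visit.** Under protocol Table D footnote 1, a participant who stops in the LTE is to "return to the NIH CC within 30 days following the last dose for the ET/EoT visit assessments". SAP Table 11 footnote 1 says the same. The footnote goes on: "Participant should resume oral calcium and active vitamin D under the supervision of the study team while the encaleret is being safely discontinued". In the ET/EoT column, Table D marks the safety and drug-monitoring laboratory panel (which includes calcium, albumin and iPTH) and the 24-hour urine.

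**Windowing.** For Period 3 and the LTE, SAP 10.12 states that "the actual visit date will be mapped to the study analysis visit as follows". Table 4 then gives study-day intervals for Months 3 to 24. Three rows, the follow-ups at 2–3, 7 and 30 days after the last dose, carry the entry "No analysis visit window applies". ET/EoT has no row. Where an NIH visit is scheduled, the selection rule is: "If the scheduled visit is an inpatient NIH visit, the NIH inpatient visit will be considered for analysis". Summaries use the analysis visit where appropriate, a phrase that is not defined.

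**Analysis set.** SAP 11.1 uses the safety analysis set for efficacy and PD. Membership needs one dose in the period, and there is no cut at the last dose.

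**Purpose.** SAP 7.0 makes durability of the effect on blood calcium a secondary LTE objective.

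**The concern.** A durability summary should show what happens while participants take the drug. Followed as written, the windowing rule gives an ET/EoT visit the label of whichever Month it falls in, whether or not the participant is still on encaleret. Values taken on conventional therapy would then be pooled, unmarked, with on-drug values.

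The bias could go either way. Losing the drug should lower cCa, while resumed calcium and active vitamin D should raise cCa and urinary calcium. For 24-hour urinary calcium the change from baseline would also lose its meaning. SAP 10.1 takes the screening collection as baseline, when participants were on their previous regimen, so an off-drug value would compare conventional therapy with conventional therapy.

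The protocol expects some participants to stop. It allows withdrawal at any point in the LTE (section 4.1), requires discontinuation for pregnancy (7.1), and provides for the case "If a participant discontinued encaleret during the CLTX-305-201 LTE for family planning purposes" (8.2.5).

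**Working it through.** **1. Reproduce Table 4.** Period 3 targets follow 6 + 7 × week, so Week 24 is day 174. LTE targets follow 174 + 30 × month: 264, 354, 444, 534, 624, 714, 804, 894. All eight agree with the SAP. Each window opens the day after the previous one closes, so days 189 to 939 are fully covered.

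**2. Is the participant off drug?** Protocol 2.2.1 gives a steady-state half-life of 11–14 hours. The fraction left at 72 hours is 2^(−72/11) = 1.1% to 2^(−72/14) = 2.8%. Thirty days is 720/14 = 51 to 720/11 = 65 half-lives. Most of the permitted lag is therefore off drug.

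**3. Where does the visit land?** Let d be the days from the last scheduled visit to the last dose, assumed uniform on 0–90. Let e be the lag from last dose to the ET/EoT visit. Scheduled visits are assumed to fall on target.
- The next window opens 46 days after a target (for example, 400 − 354) and closes 135 days after it (489 − 354). Since d + e is at most 120, the visit cannot overshoot that window.
- Share in the next window: P(d + e ≥ 46) = (44 + e)/90.
- At e = 15: 59/90 = 66%. At e = 30: 74/90 = 82%.
- In these cases the window's own scheduled visit was not reached on drug.
- The first interval differs: Month 3 opens 189 − 174 = 15 days after the Week 24 target, so every visit with e ≥ 15 lands in Month 3. Over all eight intervals the shares are (7 × 59 + 90)/720 = 70% and (7 × 74 + 90)/720 = 84%.

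**4. Full enumeration.** Every last-dose day from 175 to 893 was combined with every lag from 0 to 30 days, giving 719 × 31 = 22,289 cases.

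| Outcome for the ET/EoT visit | Cases | Share |
|---|---|---|
| Only value in its LTE window | 15,457 | 69.3% |
| Shares a Month 6/12/18/24 window with an on-drug NIH visit | 2,883 | 12.9% |
| Shares a Month 3/9/15/21 window and loses to the on-drug visit nearer target | 3,844 | 17.2% |
| Before day 189, where Table 4 starts | 105 | 0.5% |

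The selection rule does not say which of two NIH visits is used in the second row. These shares include lags near zero, so they describe where the visit is placed, not how often it is off drug.

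Examples: last dose on day 380 and visit on day 410 gives Month 9. Last dose on day 500 and visit on day 530 gives Month 12, four days from target.

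**5. Weight of one value.** With n contributors the weight is 1/n. The protocol synopsis allows up to 16 in the treatment phase, so it is at least 1/16 = 6.25%. It would be 10% at n = 10 and 12.5% at n = 8; those two values of n are assumptions.

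**6. Consistency within the SAP.** The 30-day follow-up is due at 30 ± 7 days, that is, days 23–37 after the last dose. The ET/EoT visit may fall on days 0–30. On days 23–30 both can occur in the same treatment state, yet only the follow-up is exempt from windowing.

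**The case against.** The best defence is that the SAP never says it windows the ET/EoT visit. That follows only by default, and the wording that analysis visits apply where appropriate leaves room for judgement. This is fair, but a programmer following the text would map the visit.

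Exposure is also narrow. Participants moving to the Phase 3 LTE stay on encaleret until enrolled. Thirty days is a maximum, and a visit at or just after the last dose still reflects the drug. LTE efficacy is secondary and descriptive, and the paired t-tests cover Periods 2 and 3 only. With so few participants, an odd value could be traced in the listings, which show recorded visit names. All of this stands and limits the size of the point.

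The text of SAP 10.13 and 10.15 was not available. Their titles, and the change-log note on subject-specific DXA and iPTH handling, make an ET/EoT rule there unlikely but do not exclude one.

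Some stronger readings are not supported:
- A reader might infer that the ET/EoT visit displaces on-drug local results in the NIH months. Local laboratory visits are scheduled at Months 3, 9, 15 and 21 with ±7-day windows, so no scheduled local result belongs in a Month 6, 12, 18 or 24 window.
- A reader might infer that the draw "collected at the NIH CC visits approximately 4 hours after the morning encaleret dose" is impossible at this visit. A visit on the last dosing day is allowed and could meet it.
- A reader might count visits held on the day of the last dose as contamination. Drug is still on board then.
- A reader might extend the point to Period 3 results. SAP 13.7.1 records no early discontinuations there.

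**Conclusion.** The gap is real and worth closing. In the text available, nothing keeps an off-drug ET/EoT visit out of the Month 3–24 efficacy and PD summaries, and the SAP treats that visit differently from a follow-up contact on the same day.

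The consequence is conditional: it arises only if someone stops encaleret in the LTE without moving to the Phase 3 LTE, and the documents give no count of such participants. The 66% and 82% figures rest on uniform withdrawal between visits, on-target scheduling and the stated lags. Each affected value carries at least 1/16 of a visit mean. No shift in mg/dL can be derived, because the documents give neither the size nor the direction of the off-drug change. No primary efficacy result and no hypothesis test is affected.

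**What to change.** Add one sentence to SAP 10.12: efficacy and PD assessments taken more than a short stated interval (for example, 1 day) after the last dose of study drug are not mapped to an LTE analysis visit. Add an ET/EoT row to Table 4 stating that no window applies to such visits.

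Report these values separately under a label such as 'ET/EoT, off treatment'. Keep safety laboratory and ECG results from the visit in the safety reporting under the same label, so that no safety data are lost. Table 3 needs no change.

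The cost is one sentence and one table row. The last-dose date is already used in the SAP's period-mapping rules (10.6 and 10.8). The downside is slightly fewer values at some LTE visits. This is a data-handling rule only and leaves participant management unchanged.
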